Severe hypoglycemia is the most feared complication of glucose-lowering medications used to treat people with diabetes. Severe hypoglycemia, defined as a blood sugar low enough to require assistance, is associated with accidents,¹ falls,^{2,3} motor vehicle accidents,¹ poor health-related quality of life,^{4,5} emotional and interpersonal challenges,⁶ chronic and acute cardiovascular disease,⁷⁻¹² dementia,¹³⁻¹⁵ and death.¹⁶⁻¹⁹ Older adults with type 2 diabetes on glucose-lowering medications are particularly vulnerable to the complications of severe hypoglycemia.²⁰ Severe hypoglycemia is also linked to hospitalization: of all emergency hospitalizations of older Americans for adverse drug events, an estimated 14% implicate insulin and 11% implicate oral hypoglycemic agents.²¹ One in four diabetes-related hospital admissions is due to hypoglycemia.²² Each year, about 11% of patients with type 2 diabetes self-report severe hypoglycemia.²³

Preventing severe hypoglycemia requires patients to recognize when hypoglycemia is imminent and act to prevent it. Many patients who are at risk for severe hypoglycemia, though, have lost the hormonal response and associated symptoms that would usually alert them to low blood sugar. Impaired awareness of hypoglycemia is acquired over time through repeated exposure to hypoglycemia. Severe hypoglycemia is 17 times more common in individuals with impaired awareness of hypoglycemia.²⁴ Current type 2 diabetes self-management training does not address impaired awareness of hypoglycemia and provides limited coaching on when and how to avoid severe hypoglycemia. Recently developed interventions can restore hypoglycemia awareness, enabling immediate action to reverse hypoglycemia and reduce severe hypoglycemia in patients with type 1 diabetes.²⁵⁻²⁹ We do not know if these interventions work in patients with type 2 diabetes.

The goal of this study is to compare the effectiveness of two evidence-based approaches for preventing severe hypoglycemia among patients with type 2 diabetes who are at high risk for severe hypoglycemia, defined as experiencing one or more severe hypoglycemic events in prior 12 months or having impaired awareness of hypoglycemia.

1b. Objectives:

1b.1 Primary objective

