The study will be at Kaiser Permanente Washington (KPWA), an integrated care and coverage system with 34 owned-and-operated clinics for nearly 700,000 members. We will recruit and retain a representative population in the study in two steps from KPWA clinics.

2b. Eligibility criteria

Inclusion criteria

Participants eligible for the trial must meet all the following inclusion criteria at baseline

- Age ≥18 years;
- Diagnosed with type 2 diabetes;
- Receiving primary care at KPWA;
- Enrollment at KPWA at baseline;
- Planning to stay with a KPWA health plan for the next 6 months;
- Current prescription for insulin or at intermediate to high risk for a severe hypoglycemia episode using the hypoglycemia risk-stratification tool developed by Karter et al and validated in the KPWA patient population;^{33,34} and
- Have history of a severe hypoglycemia episode in the prior 12 months or impaired awareness of hypoglycemia based on Gold score.^{35,36}

Exclusion criteria

Any of the following criteria at baseline exclude participation in the study:

- Unable to give informed consent;
- Unable to speak or read English;
- Unable or unwilling to attend online or telephone educational sessions, follow up calls, or to complete outcome assessments;
- Prior diagnosis of dementia, severe psychiatric conditions with psychosis, severe cognitive impairment;
- Currently living in nursing home or under hospice care;
- Current use at baseline of Continuous Glucose Monitor;
- Pregnant or planning to become pregnant.

2c. Interventions

Randomization will be at the individual level. Participants will be assigned to one of the two following interventions.

2c.1. Proactive care management

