2d.2 Secondary outcome measures

- Outcomes measured by Continuous Glucose Monitor, over 10 days, at baseline and 14-month assessment:
 - Percent time with biochemical hypoglycemia (<54 mg/dL);
 - Number of Level 2 biochemical hypoglycemic events (15 or more minutes <54 mg/dL).
 - Percent time biochemical hypoglycemia (< 70 mg/dL)
 - Number of level 1 hypoglycemic events (≥ 15 minutes at 54 - 69 mg/dL)
 - Number of nocturnal hypoglycemic events (≥ 15 minutes < 70 mg/dL between midnight and 6 am)
 - Percent time 70 to 180 mg/dL
 - Percent time above 180 mg/dL
 - Percent time above 250 mg/dL
 - Average blood glucoses, mg/dL
 - Standard deviation of glucose
 - Coefficient of variation for glucose (%CV)
 - Glucose management indicator
- Outcomes measured by self-report survey at baseline, 6, 10, and 14 months:
 - Number of severe hypoglycemic events in prior 4 months;
 - Hypoglycemia unawareness measured by the single item Gold survey;^{35,36}
 - Number of symptomatic⁴⁸ hypoglycemic events in the prior 4 weeks;⁴⁶
 - Fear of hypoglycemia using the Hypoglycemia Fear Survey-II;⁴⁹
 - Number of nocturnal hypoglycemia events (defined as “during sleep”) during past 6 months;⁵⁰
 - Diabetes and hypoglycemia knowledge with the revised Diabetes Knowledge Test;⁵¹
 - Diabetes self-efficacy using the 8-item Diabetes Self-Efficacy scale.⁵²

- Outcomes defined based on data collected from the EHR:
 - Hemoglobin A1c (HbA1c). The most recent HbA1c measures in the 12 months before baseline will be used for the baseline measure. Most recent measures within the past 3 months will be collected at 14 months. If the participant has not had an HbA1c within the past 3 months at 14 months, they will be asked to have one for the study.
 - Hypoglycemia-related healthcare utilization: total number urgent care, emergency department and inpatient visits for hypoglycemia as primary or principal diagnosis.

Figure 2 shows the relationship between outcome measures and study activities. Due to cost and participant burden, we will collect CGM measures only at baseline and at 14 months. We will measure all secondary outcomes including potential mediators of the intervention, at 6, 10 and 14 months after baseline assessment to identify potential early vs. later effects of the intervention.³²

Outcome Measures and Study Activities

Enrollment call,
Baseline Measures

[figure not shown]

Figure 2: Outcome measures and study activities

2e. Participant timeline

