- **EHR data** will be extracted by the study programmer from automated administrative and EHR data sources, including the KPHRI Data Warehouse, a research-centric repository of datasets maintained by the Research Institute. Data are stored in Teradata, SQL Server, and SAS format and cover enrollment, demographics, diagnoses and procedures, vital signs, pharmacy, lab tests, costs. A rich collection of powerful SAS macros can be used in conjunction with the KPHRI data. KPHRI data warehouse content and usage are documented by a wiki-based system authored by the data warehouse's architects, managers, and users. Access and security for electronic data sources are described below in Section 3. Ethics and Dissemination, Confidentiality.

4c. Statistical methods

Comparative effectiveness analyses will apply intent-to-treat principles, with study participants analyzed based on randomization group, regardless of intervention received. To assess comparability across study groups, we will summarize demographic characteristics and responses to baseline surveys in the two comparison groups. The preliminary analysis plan defines the primary outcome as a binary indicator for whether or not (yes/no) the participant self-reported having had a severe hypoglycemia event in the prior 12-months, assessed 14 months after baseline. We will estimate relative risk of severe hypoglycemia in the MyHC-T2D group vs. proactive care management group by fitting a modified Poisson regression model with the binary self-report measure as the dependent variable and randomization group as the independent variable. Models will adjust for age, sex, risk score, and the number of self-reported severe hypoglycemic events in the 12 months prior to baseline. Models will be fit using generalized estimating equations (GEE) and robust variance estimation to account for correlation due to patient clustering in the intervention arm within group training session cohorts, and the misspecified mean-variance relationship in using Poisson regression for a binary outcome.

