Prior to conducting analysis of 14-month outcomes, we will look at the baseline distribution of the self-reported number of severe hypoglycemic events in the prior 12-months collected at baseline. If more than 60% of enrolled patients report 2 or more events, we will revise the primary outcome to be defined as the self-reported *number* of severe hypoglycemic events in the past 12-months, measured at 14-months post baseline (a count rather than a binary outcome and fit a Poisson regression model to estimate the rate ratio for severe hypoglycemia events for the MyHC-T2D group relative to the care management group. We will assess model fit, and consider zero-inflated models as an alternative, if the number of participants reporting zero events violates distributional assumptions of the Poisson model. If primary analyses use the binary outcome measure (i.e. fewer than 60% of patients report 2 or more events in the 12-months prior to baseline), but 40% or more of respondents report 2 or more events at 14-months, we will do a secondary analysis with the count variable as the outcome.

Generalized linear regression models estimated with GEE and robust sandwich errors will also be used to estimate intervention effects on secondary outcomes, with link function and error distribution appropriate for each outcome. For secondary outcomes measured at multiple follow-up time points (6-, 10- and 14-months post-baseline), we will fit a single regression model that includes outcome measures from all follow-up time points. Models will include indicator variables for time, intervention group, and interaction terms between these variables, to estimate intervention effects at each time point. Models will adjust for age, sex, risk score and the baseline measure of the outcome. For hypoglycemia-related health care utilization (urgent care and emergency department visits, hospital admits), we will follow a similar analytic plan as the primary outcome, including the process to determine whether to model these outcomes as binary or count variables.

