Standards for Preventing and Handling Missing Data. Outreach with repeated calls will maximize response rates of follow-up phone surveys. Response rates and data collection will be monitored and if attrition is greater than 10%, statistical methods will account for potential selection bias. We will compare baseline characteristics of responders and non-responders and consider multiple imputation or inverse probability weighting (IPW) to account for potential bias due to missing data.

Addressing HTE standards.

Exploratory analyses will assess whether treatment effects vary by patient characteristics including age (under 75 years vs. 75 years and older), sex, race/ethnicity, comorbidities, insulin use and/or sulfonylurea use, baseline IAH presence, and baseline SH history. We will include interaction terms between randomization group and these characteristics in the primary and secondary outcome models to estimate comparative effectiveness by subgroup.

We provide a brief description of the power we estimate we will have for some subgroup analyses. For those with minority racial and ethnic backgrounds (approximately 30% of participants), we will have 90% power to detect a 39% difference and 80% power to detect a 35% difference in the rate of severe hypoglycemia between comparators for this subgroup. For females (approximately 50% of participants) and those the 65 years of age or older (approximately 50% of participants), we will have 90% power to detect a 31% difference in the rate of severe hypoglycemia and 80% power to detect 27% difference. All of these effect sizes are smaller than those in the MyHC-T2D study in patients with type 1 diabetes.³⁴

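### The primary model leaves out baseline hypoglycemia awareness; adding it as a prespecified covariate costs almost nothing and may gain a little precision

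*Combined protocol and SAP*

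**What the plan says.** Section 4c (Statistical methods) fits a modified Poisson model to the yes/no primary outcome, with randomization group and these covariates: "Models will adjust for age, sex, risk score, and the number of self-reported severe hypoglycemic events in the 12 months prior to baseline". Neither the Gold score nor impaired awareness of hypoglycemia (IAH) appears.

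Awareness appears elsewhere in the plan:

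- **Entry (2b):** "Have history of a severe hypoglycemia episode in the prior 12 months or impaired awareness of hypoglycemia based on Gold score". It is one of two alternatives, so a participant may have either or both.
- **Measurement (2d.2):** under "Outcomes measured by self-report survey at baseline, 6, 10, and 14 months" the list includes "Hypoglycemia unawareness measured by the single item Gold survey". A baseline value is therefore planned for every participant.
- **Allocation (3a):** strata are age group and hypoglycemia risk score. Awareness is not a stratum.
- **Background (1a):** "Severe hypoglycemia is 17 times more common in individuals with impaired awareness of hypoglycemia".
- **Subgroup analyses (4c):** the exploratory effect modifiers include "baseline IAH presence, and baseline SH history", and "We will include interaction terms between randomization group and these characteristics in the primary and secondary outcome models".
- **Secondary outcomes (4c):** "Models will adjust for age, sex, risk score and the baseline measure of the outcome", so the Gold score as an outcome is adjusted for its own baseline.

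**The concern.** The trial is built around awareness: it is a route into the study, a target of the intervention and a proposed mediator. Yet in the primary comparison its balance between arms is left to chance. Stratification does not secure it, and the primary covariate list does not correct for it. The exploratory interaction models do contain baseline IAH, but they leave the primary estimate as it is.

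The prior event count does not make awareness redundant. Under the entry rule everyone with a zero count has IAH, while those with one or more events are a mixture. A zero count is therefore not a clean marker of low risk, and a single linear count term may carry the two routes poorly.

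Two things are at stake in a planned analysis of 204 patients: some precision of the relative risk, and the shift in the estimate if the arms happen to differ in awareness. Validity is not at stake.

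**Working it through.** **1. The plan's own power (2f).** Inputs: 256 × 0.8 = 204.8, taken as 204, or 102 per arm; control risk 60%; alpha 0.05, taken as two-sided. Power = Φ{[d − 1.96·√(2p̄(1−p̄)/n)] / √([p1(1−p1)+p2(1−p2)]/n)}.

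- 60% vs 37.4%: d = 0.226, p̄ = 0.487; (0.226 − 1.96 × 0.0700)/0.0682 = 1.30, power 90.4% (stated 90%).
- 60% vs 40.3%: d = 0.197, p̄ = 0.5015; (0.197 − 1.96 × 0.0700)/0.0686 = 0.87, power 80.8% (stated 80%).

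The plan's figures reproduce. They are unadjusted, so they do not depend on the covariate list.

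**2. Can the 17-fold figure be used inside the trial?** Let w be the share with IAH and r their risk, with aware participants at r/17. A mean control risk of 60% requires w·r + (1−w)·r/17 = 0.60. Since r ≤ 1, w ≥ (0.60 − 1/17)/(16/17) = 57.5%, and the aware risk is at most 1/17 = 5.9%. Under 2b, every aware participant has had a severe event in the past 12 months, so so low a risk is not credible.

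**3. What awareness adds once the count is in the model.** The documents give no in-trial IAH share or association, so these inputs are assumed: a 17-fold rate ratio in the source population, source IAH prevalence 10% or 20%, gamma frailty with variance 1 or 3 (shape 1 or about 0.3), entry on a prior event or IAH, and control risk set to 60%. The treated risk is 40.3%. Each scenario has 204 patients and 2,500 trials, and the baseline count is capped at 10. Variance change = (SE with IAH / SE without)² − 1.

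| Source IAH, frailty variance | IAH share in trial | Risk: IAH / aware | SE: count → count + IAH | Variance change | Power: count → count + IAH |
|---|---|---|---|---|---|
| 10%, 1 | 25% | 0.896 / 0.502 | 0.1465 → 0.1459 | -0.8% | 82.4% → 82.6% |
| 10%, 3 | 31% | 0.653 / 0.575 | 0.1407 → 0.1401 | -0.9% | 84.1% → 84.0% |
| 20%, 1 | 55% | 0.814 / 0.338 | 0.1432 → 0.1378 | -7.4% | 83.9% → 87.2% |
| 20%, 3 | 52% | 0.643 / 0.555 | 0.1361 → 0.1362 | +0.1% | 86.0% → 85.9% |

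The source 17-fold rate ratio shrinks to an in-trial risk ratio of about 1.1 to 2.4. The estimated treatment relative risk is about 0.67 in every model. Monte Carlo error on each power figure is about √(0.85 × 0.15/2500) = 0.7 points.

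**4. Wider assumptions.** Further simulations of this kind, with lower source rate ratios as well as 17 and with an uncapped count, gave a variance change of about +1% to -12% and a power change of about 0 to 6 points. An uncapped count leaves more for awareness to explain. In a set of 24 scenarios the most favourable result was -17%; rate ratios of 3-5 gave reductions of about 0-4%, and 17-fold with strong heterogeneity (shape 0.3) about 0-3%. In terms of power, starting from 80%: Φ(2.80/√0.96 − 1.96) ≈ 82% for a 4% reduction and Φ(2.80/√0.83 − 1.96) ≈ 87% for 17%.

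**5. Chance imbalance.** The standard deviation of the between-arm difference in IAH share is √(2w(1−w)/102): 6.1 points at w = 0.25 and 7.0 points at w = 0.55. At a 1-in-20 imbalance (1.96 SD, about 12 to 14 points), the relative risk from the count-only model shifted by about 1-8% in either direction across eight scenarios. With IAH added the shift was about 1% or less.

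**6. Validity.** With IAH as the only covariate, simulated type I error under no treatment effect was 3.8% to 5.5%, with or without the term.

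**The case against.** A reader might infer that the protocol itself declares awareness a 17-fold risk factor for these patients, so that leaving it out biases the primary result or seriously weakens the trial. The documents do not support that. The sentence in 1a is an unconditional background comparison. It does not condition on prior events and does not describe the enrolled sample. Nor does the protocol say that two participants with the same prior count but different awareness have different future risk; at a count of zero, no such pair exists.

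Even the direction is open. With source rate ratios of 3-5 and strong heterogeneity, simulated participants with IAH had lower risk than aware ones (0.46-0.56 against 0.63-0.73), because aware patients enter only through a recent event.

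The rest of the objection also has force. The plan already adjusts for both stratification factors and for the baseline count of the outcome event. Section 4c tabulates baseline survey responses by arm, so an imbalance would be seen. The simulations leave out age, sex, risk score and session clustering; if risk score is correlated with awareness, the gain shrinks. Recruitment is complete and the biostatisticians may see data by arm, so a late change to the primary model could look post hoc.

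All of this limits the size and the timing of the point. It does not remove it: the value is planned for collection, its possible cost is about 1% of variance, and seeing an imbalance in a table does not correct the estimate.

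**Conclusion.** The omission is a defensible choice that can be improved cheaply. It does not bias the relative risk or raise the type I error in the randomized comparison. With the prior count in the model, adding yes/no IAH would change the variance of the log relative risk by about +1% to -12% (-17% at the most favourable), usually a reduction of 0-4%, and power by about 0 to 6 points. It would also remove most of the shift from an unlucky imbalance.

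These ranges rest on assumed prevalence, rate ratio and heterogeneity, none of which the documents supply, and they apply to the binary primary outcome. A gain near zero is fully compatible with the documents. This is a minor suggestion.

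**What to change.** Add baseline awareness to the primary model in 4c as a yes/no IAH term, using the Gold cut-off applied for eligibility. That is the form that was simulated; a linear Gold score was not. Section 2b does not give the cut-off, so the amendment should state it, and should also say how a missing baseline Gold item is handled. Date and fix the change before any 14-month outcome is analysed by arm. If that can no longer be shown, keep the current primary model and report the awareness-adjusted model as a declared sensitivity analysis.

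The cost is one degree of freedom, up to about 1% more variance if awareness turns out not to be prognostic, and an amendment to the analysis plan after recruitment is complete. No new data are needed.
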